This study will include patients age 7 years or older with mutations in *RYR1* (confirmed by previous genetic testing), who are not currently taking antioxidants, and who are able and willing to perform all procedures at the time of enrollment. Children under age 7 may not be

able to successfully follow instructions for outcome measure testing. The accrual ceiling is 100. Withdrawals/dropouts will not be replaced. The target number of completers is 76.

Sixty to 100 age-matched healthy volunteers will be recruited.

NIH employees may participate. The NIH Information Sheet on Staff Research Participation will be provided to any staff member wishing to participate in this study (see Appendix L).

b. Inclusion criteria

Patients:

- Have a confirmed genetic diagnosis of RYR1-related myopathy, including congenital myopathy, OR have a clinical diagnosis of RYR1-related myopathy and a family member with a confirmed genetic diagnosis of RYR1-related myopathy
- Ambulatory.
- 7 years of age or older.
- Preferred: The affected subject has a previous muscle biopsy with available report confirming RYR1-related myopathy histopathology.

Healthy Volunteers:

- Ages 7 and older (15-25 7-12 year olds, 15-25 13-17 year olds, 15-25 18-40 year olds, 15-25 41 and older) without medical condition resulting in or complaints of muscle weakness and/or fatigue.
- The ability to provide consent.

c. Exclusion criteria

Patients:

- Adults who cannot provide their own consent and pediatric participants who do not have a parent able to provide consent
- Patients with a history of liver disease (Liver Function Tests will be collected at baseline and at each study visit as a precautionary measure). Liver disease is defined as moderate to severe hepatic impairment based on the following:
ALT \geq 8x upper limit of normal (ULN) with total bilirubin 2x ULN (plus >35% 'direct' bilirubin) and/or INR >1.5
or
GGT > 2-3x ULN with bilirubin 2x ULN (plus >35% 'direct' bilirubin) and/or INR >1.5
GGT >2-3x ULN and INR >1.5
- Patients with a history of peptic ulcers, gag reflex depression, and esophageal varices. Patients with gastrostomy tubes may be considered for participation, in the case of gag reflex depression or other swallowing or feeding difficulties.

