Participants with fear of confined spaces may become anxious during an MRI. Those with back problems or significant contractures may have pain or discomfort from lying in the scanner. The noise from the scanner is loud enough to damage hearing, especially in participants who already have hearing loss. Everyone having a MRI scan will be fitted with hearing protection. There are no known long-term risks of MRI scans. Participants may learn pregnancy status through required pregnancy testing.

Physical therapy: 6 Minute Walk, Motor Function Measure³², timed tests, and Myotools tests are patient self-limiting tests with minimal risk and discomfort. Participants may become fatigued.

Biodex: Biodex may produce strain on the heart, muscles, and joints. The following contraindications will be ruled out prior to proceeding with Biodex: history of CAD and/or valvular disease, hypertension (>140/90), aneurysm, severe osteoporosis (BMD >-2.5 standard deviations and history of pathological fracture), acute sprain or strain, unstable joint/bone, knee pain, quadriceps tendonitis, moderate-severe joint effusion, extremely limited joint range of motion, severe pain, soft tissue healing constraints, unable to follow commands appropriately, unable to perform desired motion. BP would be taken immediately prior to testing to confirm appropriate parameters.

Arterial Occlusion Muscle Oxygenation Capacity Test: The only known risk associated with arterial occlusion is discomfort. This procedure will not be performed on individuals who have disorders predisposing them to thrombosis, as a precaution. Arterial occlusion has been performed in patients with various myopathies, including Duchenne muscular dystrophy, and there were no reported adverse events (Sander et al., 2000). There are no published data to our knowledge regarding the incidence of a clot being formed or dislodged due to this procedure. However, due to the nature of the procedure, this is a theoretical risk. Thus, we are excluding subjects with disorders predisposing them to thrombosis, as a precaution. This risk also applies to healthy volunteers.

Phlebotomy: Participants may have some discomfort and bruising at the site of needle entry. There is a very small risk of fainting. Infection in the area of the needle insertion is rare. This risk also applies to healthy volunteers.

Genetic Testing: Risks of sharing genomic data may include the possibility of re-identification.

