Investigators will evaluate participants for any foreseeable safety concerns before study procedures are performed. Investigators will allow participants to miss individual procedures (other than the two primary outcome measures— urine collection for 15 F2t-isoprostane levels and 6MWT), at one or all study visits, if safety concerns arise. Examples include: If a participant has a recent history of knee dislocation or knee injury, that participant will be excluded from the Biodex procedure. If a participant has an increased risk of blood clotting, that participant will not perform the arterial occlusion test. If a participant is at NIH and recently recovered from a rhabdomyolysis crisis, that participant will not perform CPET at that visit, but may perform CPET at following visits, if deemed safe at that time. If a participant has certain types of metal in their body, that participant will not perform the MRI procedure at any visit. Investigators will ask participants about potential safety concerns for each procedure and participants are also asked to inform study investigators about potential risk factors in the consent. Investigators will have a participant miss certain non-primary outcome measure procedures, due to safety concerns, at their discretion. Participants will remain enrolled in the study if they are able to safely perform the two primary outcome measures and are also able to safely consume the study medication/placebo, given the expected side effects. [name] can withdraw a participant, at any time, if she believes continuation is not in their best medical interest, or if the participant is unable to comply with the study.

For monitoring for NAC administration, please see previous section under “Steps Taken to Minimize Risk”.

For other individual monitoring plans, please see previous section under “Steps Taken to Minimize Risk.”

Criteria for stopping procedures in an individual include:

If a patient reports Grade 3 side effects for diarrhea, nausea, vomiting, constipation, or abdominal pain, or any other Grade 3 side effect, according to the NCI Common Terminology

Criteria for Adverse Events v.3.0, we will discontinue their participation.

Criteria for individual subject withdrawal from the study

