If Grade 1 side effects are reported, we will monitor them by phone and/or email and keep them on the drug. If Grade 2 side effects are reported, we will discontinue drug until the side effect resolves and then resume administration with careful observation for reoccurrence. Please see Section 7 under “Steps Taken to Minimize Risks” for further details.

9. Outcome Measures

Outcome Measures	Aim 1=Oxidative Stress	Aim 2=Fatigability, Fatigue
Primary	urine 15-F2t-isoprostane	6MWT
Secondary	DCFH assay in muscle biopsy (6 and 12 months only), blood GSH	Timed function tests; Biodex; PROMIS, FACIT, MFI, MRI, MFM, NeuroQoL scales, Myotools
Exploratory	Anaerobic threshold, NIRS; secreted ER calcium monitoring proteins (SERCaMPs) assay in blood and muscle	CPET, EIM, salivary FBI, melatonin, cortisol and DHEA; QoL qualitative interview

Aim 1

Blood and urine samples will be collected **at each visit**. Samples will be analyzed at NIH or shipped to [name] for urine isoprostane analysis at the Vanderbilt University Ecosinoid Core Facility. De-identified blood samples will also be shipped to Emory University to assay glutathione via mass spectrometry. Needle muscle biopsy will be performed at six and twelve months on up to 20 willing adult participants only.

GSH: Mass spectrometry, fluorescent, and colorimetric assays will be used to measure levels of reduced (GSH) and oxidized (GSSG) glutathione in plasma and whole blood to observe changes in oxidative stress. These assays include deproteinization, derivatization, and/or catalytic reactions.

DCFH: As in the preliminary studies above, DCFH will be used on participant muscle biopsies to analyze intracellular oxidant activity [H2DCFDA (H2-DCF, DCF)].

15-isoprostane-F2: Urine will be assayed for 15-isoprostane-F2, which is formed when arachidonic acid reacts with ROS. A validated GC-MS/MS method will be used to quantify 14-isoprostane-F2.

Anaerobic threshold: Anaerobic threshold and time to anaerobic threshold will be extrapolated from data obtained during CPET.

NIRS: Percentage of local muscle oxygen and oxygen consumption as determined by tissue oxygen index (TOI) and hemoglobin.

SERCaMPs: Measurement of protein level of *Gaussia* luciferase-based secreted ER calcium-monitoring protein (SERCaMP) in blood, primary muscle cells and/or cell lines. (Hendersen et al. 2015)

Aim 2

All procedures for Aim 2 will be performed at the NIH Clinical Center **at each visit**.

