CPET: VO₂ peak, peak power, test duration of entire test, time to AT, work efficiency (VO₂ work rate slope), and ventilator equivalent (VE/VO₂) will be obtained.

EIM: An EIM will be used to measure skeletal muscle health. Resistance, reactance and phase of multiple muscles will be measured.

6MWT: Meters walked in 6 minutes will be recorded (to the nearest meter). Distance in meters will be recorded at each minute interval. Speed will be calculated.

Timed tests: Participants will be timed in the performance of the following: 10 meter walk test, supine to stand, ascend 4 stairs, descend 4 stairs. They will be graded on an ordinal scale.

Myotools: Force required for participants to squeeze the grip dynamometer and pinch the pinch gauge. The best effort of 3 trials will be recorded for grip and pinch strength.

Biodex: Biodex will be used to test muscle groups using a dynamic sub-max fatigue test with a repetitive motion. Blood pressure will be taken prior to testing to confirm the patient is not hypertensive (>140/90). Outcome measures will include peak torque measured in newton meters and number of repetitions to 50% decline in peak torque.

Arterial Occlusion Muscle Oxygenation Capacity Test: The tissue saturation index will be calculated as $TOI = [O_2-Hb] / Tot-Hb$. The rate of decline and rise in TOI will be the main muscle tissue saturation measures.

MFM: The final outcome is a percentage based score of each domain and the total score.

PROMIS, FACIT, MFI, NeuroQoL: Questionnaires will be scored based on each scale's requirements.

MRI: The outcomes will be muscle mass via T1, fat composition via T1 to T2 comparison, water composition via T1 to T2 comparison and chemical composition (lipids) via MRS.

Saliva collection: FBI, melatonin, cortisol and DHEA levels will be obtained.

Qualitative interview: Responses to the interview will be obtained and major themes will be identified.

10. Statistical Analysis

a. Analysis of data/ study outcomes

Natural history study (Phase 1 of protocol):

During the natural history phase of the study, we will take one look at the data prior to the final analysis with the following two approaches:

- 1) After 30 participants complete their baseline visit, we will compare their baseline outcome measure values against healthy controls. For the primary outcomes, 15-F2t-isoprostane and 6MWT distance will be compared against healthy individuals. This analysis will be repeated when all baseline visits are completed.

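### The bone-density limit in the Biodex contraindication list has its inequality reversed (low severity)

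*Protocol*

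**What the plan says.** The Biodex paragraph of Protocol Section 7 warns of strain on the heart, muscles and joints and then sets a screen: "The following contraindications will be ruled out prior to proceeding with Biodex". The list that follows has 14 items. The bone item is "severe osteoporosis (BMD >-2.5 standard deviations and history of pathological fracture", closing with a parenthesis. It is preceded by "history of CAD and/or valvular disease, hypertension (>140/90), aneurysm" and followed by "acute sprain or strain, unstable joint/bone, knee pain".

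Only two of the 14 items carry a numeric limit: blood pressure and bone density. The Biodex entries in Sections 4d and 9 repeat the blood-pressure limit: "Blood pressure will be taken prior to testing to confirm the patient is not hypertensive (>140/90". Neither repeats or corrects the bone-density limit, and nor does any other part of the text available for this review.

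Section 4d makes every procedure except the biopsy mandatory unless contraindicated. Section 9 places the Aim 2 procedures, Biodex among them, at every visit. The outcome table there puts Biodex in the secondary row for Aim 2: "Timed function tests; Biodex; PROMIS, FACIT, MFI, MRI, MFM, NeuroQoL scales, Myotools".

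**The concern.** The condition named and the numeric rule attached to it point in opposite directions. Severe osteoporosis is a state of low bone density, and a limit of -2.5 SD is meant to catch values far below the reference mean. With a greater-than sign, the rule catches everyone on the other side.

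This matters because the list is a working safety screen and not background text. Contraindication is the protocol's stated ground for leaving out an otherwise required procedure. Someone applying the parenthesis literally would clear, on this item, the fracture patients with the weakest bone and would hold back those whose bone density lies above the limit. What is at stake is participant safety at a secondary assessment, and to a lesser degree which patients contribute Biodex data. No error rate, power figure or primary analysis depends on it.

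**Working it through.** There is no plan figure to reproduce. The check is the direction of one inequality.

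**Inputs** (Protocol Section 7, Biodex)
- Rule as written: bar if BMD > -2.5 SD and there is a history of pathological fracture.
- Role: conditions that must be absent before the test.
- Items in the list: 14, of which 2 have a numeric limit.

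**What the sign means in this protocol.** For blood pressure, a value above 140/90 bars the patient, so the greater-than sign has its ordinary arithmetic meaning in the same list. Where a low value is the problem, the protocol uses a less-than sign: Section 3c excludes FEV1 below 40% of predicted and gives haemoglobin below 8 g/dl as an example of a disqualifying condition. The bone-density item departs from that usage.

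**Applying the rule to a patient who has had a pathological fracture**

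| BMD (SD) | As written: > -2.5 | Corrected: <= -2.5 | Corrected: < -2.5 |
|---|---|---|---|
| -3.0 | -3.0 > -2.5 is false: not barred | barred | barred |
| -2.5 | -2.5 > -2.5 is false: not barred | barred | not barred |
| -1.0 | -1.0 > -2.5 is true: barred | not barred | not barred |

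At -3.0 and -1.0 SD the written rule gives the opposite answer to either corrected form. The choice between the two corrected forms matters only at exactly -2.5 SD.

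**Scale of the bone-density part alone.** If SD scores are assumed to be standard normal in a reference population (the documents do not say so), P(Z > -2.5) = 0.9938 and P(Z <= -2.5) = 0.0062. The written sign therefore covers about 99.4% of that population, where the intended one covers about 0.6%. These shares ignore the fracture condition, which must also be met, so they do not estimate how many trial patients are affected.

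**The case against.** The strongest reply is that this is a slip of one character with an obvious meaning. The item names severe osteoporosis and requires a pathological fracture. A clinician would probably read the parenthesis as more than 2.5 SD below the mean, and on that reading a fracture patient at -3.0 SD plainly has the named condition. The blood-pressure comparison is also imperfect, because a positive limit does not prove what the author meant by the same sign before a negative one. These points make harm unlikely, but they do not make the rule correct. A reader has to override the symbol to reach the intended screen.

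Other protections overlap. Unstable bone is a separate item in the list, and Section 8 states: "Investigators will evaluate participants for any foreseeable safety concerns before study procedures are performed". It also lets participants miss non-primary procedures for safety reasons. These are real but partial backups, since neither sets a limit for low bone density.

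The available text schedules no bone-density measurement, so the item could act only through medical history or outside records. Section 10b says the study is being closed to data analysis, so no further Biodex screening is evident. Both points stand and keep the severity low.

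A symbol misread when the PDF was converted cannot be fully excluded. Nothing suggests one, as other greater-than and less-than signs in the protocol read sensibly. Part of Section 7 and the eligibility checklist (Appendix E) were not available, so the screen used in practice cannot be seen. That absence is not counted against the plan.

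**Conclusion.** The concern holds, at low severity. The written limit contradicts the condition it is meant to define and gives the opposite screening decision at both -3.0 and -1.0 SD for a patient with a pathological fracture. This is a drafting error in an operative safety criterion, confined to 1 of 14 contraindications. The number of patients affected is not given and may be zero.

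The conclusion rests on reading the sign arithmetically, as the protocol does elsewhere, and on the text extraction being faithful at this point. It does not depend on whether the corrected limit includes -2.5 SD itself. The primary outcomes, sample size and primary analysis are unaffected.

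**What to change.** In the Biodex paragraph of Protocol Section 7, change the limit to BMD <= -2.5 standard deviations, keeping the fracture condition. The inclusive boundary is an assumption, and the medical lead should confirm whether <= or < is intended.

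While the line is open, the medical lead could also name the score (T- or Z-score), because patients are enrolled from "7 years of age or older". That is a clarification only, and the finding does not depend on it.

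The cost is one sign and, if the clarification is adopted, one word. No new procedure, data collection or record review is needed. With the study closed to data analysis, the benefit is a correct protocol of record and a limit that is not copied in error into later work.

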In our proposed study, after participants receive drug or placebo effervescent tablets at the 6-month visit, they will be monitored at NIH for 2 consecutive days as an extra precaution to rule out rhinorrhea, stomatitis, urticarial/ facial flushing, rash, pruritus, hives, coughing, headache, drowsiness, clamminess, chest tightness, bronchoconstriction, and hypotension, which are the most severe potential side effects of inhaled or injected NAC. This monitoring will include being observed in the outpatient clinic for 2 hours after their initial dose, including having vitals signs measured. The second day of observation at NIH will include an outpatient clinic visit with vital signs. If at any other time, the participant notices any symptoms, they will be directed to contact our onsite nurses. A Licensed Care Provider will then call them at one and three weeks to monitor adverse reactions. We will then monitor participants monthly (2, 3, 4, and 5 months) by phone and/or email, primarily for gastrointestinal symptoms, which are the main symptoms of PharmaNAC effervescent tablets. If a patient reports any of the side effects that have already been reported (rash, chest tightness with coughing, hives, or hypotension), they will be advised to stop taking the study medication immediately. They will only restart the study medication after discussing their symptoms with the PI. Patients are also asked, in the consent form, to limit their alcohol consumption to no more than 2 alcoholic drinks per day as excess alcohol consumption may interact with glutathione levels. Participants are informed to call study investigators immediately if they have any problems or side effects and are provided with contact information. They are instructed to visit the emergency room if they have a possible allergic reaction or a serious or life-threatening emergency. They are expected to tell the ER staff that they are in a research study and ask the emergency personnel call the research nurse. Participants are instructed to continue under the care of their local clinicians throughout participation. Participants are provided with a “NAC Information Letter for Clinicians” (Appendix F) to share with their home clinicians. This letter provides study drug information and information about possible side effects.

If a patient reports Grade 3 side effects for diarrhea, nausea, vomiting, constipation, or abdominal pain, or any other Grade 3 side effect, according to the NCI Common Terminology Criteria for Adverse Events v.3.0, we will discontinue their participation. If Grade 1 side effects are reported, we will monitor them by phone and/or email and keep them on the drug. If Grade 2 side effects are reported, we will discontinue drug until the side effect resolves and then resume administration with careful observation for reoccurrence. Monitoring for grades 1 and 2 side effects will include weekly phone calls and/or emails until symptoms subside. If symptoms worsen subjects will visit their primary care physician. Subjects who experience grade 3 symptoms will receive an assessment by our healthcare provider and will be advised to schedule a prompt appointment with their local healthcare provider. We will also encourage them to contact us at any time with questions or concerns.

We will offer an evaluation at NIH for any participant who would like to return for an evaluation of side effects, such as, but not limited to, local participants. This evaluation will include a history and physical examination, discussion with the medical advisory investigator,

and appropriate consults, for example a GI consult.

An informational letter (Appendix F) to the participant's physician will be given to each subject to give to their primary care provider.

8. Subject Safety Monitoring

For CPET, there is literature to suggest that participants with mutations in RYR1 are susceptible to exertional rhabdomyolysis or heatstroke with extreme exercise. We will not be having the patients do extreme exercise, but will take precautions to be ready to prevent these susceptibilities just in case. The precautions include having the CPET performed in a cool room with a fan blowing on the patient, while monitoring the patient's temperature. We will ask the patient if they are experiencing cramping, stiffness, or pain throughout the procedure. If the answer is yes, or if their temperature exceeds 101 degrees Fahrenheit, we will stop the exercise immediately. A STAT blood draw will be done to check serum creatine kinase and potassium levels and urine will be collected for myoglobin. If the patient is medically unwell, the patient will be admitted to the day hospital and an IV will be started immediately for hydration. If the CK, potassium and urine myoglobin levels are elevated suggestive of rhabdomyolysis, they will be treated with sodium bicarbonate and monitored until the rhabdomyolysis is safely resolved.

Investigators will evaluate participants for any foreseeable safety concerns before study procedures are performed. Investigators will allow participants to miss individual procedures (other than the two primary outcome measures— urine collection for 15 F2t-isoprostane levels and 6MWT), at one or all study visits, if safety concerns arise. Examples include: If a participant has a recent history of knee dislocation or knee injury, that participant will be excluded from the Biodex procedure. If a participant has an increased risk of blood clotting, that participant will not perform the arterial occlusion test. If a participant is at NIH and recently recovered from a rhabdomyolysis crisis, that participant will not perform CPET at that visit, but may perform CPET at following visits, if deemed safe at that time. If a participant has certain types of metal in their body, that participant will not perform the MRI procedure at any visit. Investigators will ask participants about potential safety concerns for each procedure and participants are also asked to inform study investigators about potential risk factors in the consent. Investigators will have a participant miss certain non-primary outcome measure procedures, due to safety concerns, at their discretion. Participants will remain enrolled in the study if they are able to safely perform the two primary outcome measures and are also able to safely consume the study medication/placebo, given the expected side effects. [name] can withdraw a participant, at any time, if she believes continuation is not in their best medical interest, or if the participant is unable to comply with the study.

For monitoring for NAC administration, please see previous section under “Steps Taken to Minimize Risk”.

For other individual monitoring plans, please see previous section under “Steps Taken to Minimize Risk.”

Criteria for stopping procedures in an individual include:

If a patient reports Grade 3 side effects for diarrhea, nausea, vomiting, constipation, or abdominal pain, or any other Grade 3 side effect, according to the NCI Common Terminology

Criteria for Adverse Events v.3.0, we will discontinue their participation.

Criteria for individual subject withdrawal from the study

If Grade 1 side effects are reported, we will monitor them by phone and/or email and keep them on the drug. If Grade 2 side effects are reported, we will discontinue drug until the side effect resolves and then resume administration with careful observation for reoccurrence. Please see Section 7 under “Steps Taken to Minimize Risks” for further details.

9. Outcome Measures

Outcome Measures	Aim 1=Oxidative Stress	Aim 2=Fatigability, Fatigue
Primary	urine 15-F2t-isoprostane	6MWT
Secondary	DCFH assay in muscle biopsy (6 and 12 months only), blood GSH	Timed function tests; Biodex; PROMIS, FACIT, MFI, MRI, MFM, NeuroQoL scales, Myotools
Exploratory	Anaerobic threshold, NIRS; secreted ER calcium monitoring proteins (SERCaMPs) assay in blood and muscle	CPET, EIM, salivary FBI, melatonin, cortisol and DHEA; QoL qualitative interview

Aim 1

Blood and urine samples will be collected **at each visit**. Samples will be analyzed at NIH or shipped to [name] for urine isoprostane analysis at the Vanderbilt University Ecosinoid Core Facility. De-identified blood samples will also be shipped to Emory University to assay glutathione via mass spectrometry. Needle muscle biopsy will be performed at six and twelve months on up to 20 willing adult participants only.

GSH: Mass spectrometry, fluorescent, and colorimetric assays will be used to measure levels of reduced (GSH) and oxidized (GSSG) glutathione in plasma and whole blood to observe changes in oxidative stress. These assays include deproteinization, derivatization, and/or catalytic reactions.

DCFH: As in the preliminary studies above, DCFH will be used on participant muscle biopsies to analyze intracellular oxidant activity [H2DCFDA (H2-DCF, DCF)].

15-isoprostane-F2: Urine will be assayed for 15-isoprostane-F2, which is formed when arachidonic acid reacts with ROS. A validated GC-MS/MS method will be used to quantify 14-isoprostane-F2.

Anaerobic threshold: Anaerobic threshold and time to anaerobic threshold will be extrapolated from data obtained during CPET.

NIRS: Percentage of local muscle oxygen and oxygen consumption as determined by tissue oxygen index (TOI) and hemoglobin.

SERCaMPs: Measurement of protein level of *Gaussia* luciferase-based secreted ER calcium-monitoring protein (SERCaMP) in blood, primary muscle cells and/or cell lines. (Hendersen et al. 2015)

Aim 2

All procedures for Aim 2 will be performed at the NIH Clinical Center **at each visit**.

CPET: VO₂ peak, peak power, test duration of entire test, time to AT, work efficiency (VO₂ work rate slope), and ventilator equivalent (VE/VO₂) will be obtained.

EIM: An EIM will be used to measure skeletal muscle health. Resistance, reactance and phase of multiple muscles will be measured.

6MWT: Meters walked in 6 minutes will be recorded (to the nearest meter). Distance in meters will be recorded at each minute interval. Speed will be calculated.

Timed tests: Participants will be timed in the performance of the following: 10 meter walk test, supine to stand, ascend 4 stairs, descend 4 stairs. They will be graded on an ordinal scale.

Myotools: Force required for participants to squeeze the grip dynamometer and pinch the pinch gauge. The best effort of 3 trials will be recorded for grip and pinch strength.

Biodex: Biodex will be used to test muscle groups using a dynamic sub-max fatigue test with a repetitive motion. Blood pressure will be taken prior to testing to confirm the patient is not hypertensive (>140/90). Outcome measures will include peak torque measured in newton meters and number of repetitions to 50% decline in peak torque.

Arterial Occlusion Muscle Oxygenation Capacity Test: The tissue saturation index will be calculated as $TOI = [O_2-Hb] / Tot-Hb$. The rate of decline and rise in TOI will be the main muscle tissue saturation measures.

MFM: The final outcome is a percentage based score of each domain and the total score.

PROMIS, FACIT, MFI, NeuroQoL: Questionnaires will be scored based on each scale's requirements.

MRI: The outcomes will be muscle mass via T1, fat composition via T1 to T2 comparison, water composition via T1 to T2 comparison and chemical composition (lipids) via MRS.

Saliva collection: FBI, melatonin, cortisol and DHEA levels will be obtained.

Qualitative interview: Responses to the interview will be obtained and major themes will be identified.

10. Statistical Analysis

a. Analysis of data/ study outcomes

Natural history study (Phase 1 of protocol):

During the natural history phase of the study, we will take one look at the data prior to the final analysis with the following two approaches:

- 1) After 30 participants complete their baseline visit, we will compare their baseline outcome measure values against healthy controls. For the primary outcomes, 15-F2t-isoprostane and 6MWT distance will be compared against healthy individuals. This analysis will be repeated when all baseline visits are completed.

Hypothesis: 15-F2t-isoprostane will be significantly increased in RYR1-RM myopathy patients compared to healthy individuals.

Hypothesis: 6MWT distance will be significantly decreased in RYR1-RM patients compared to healthy individuals.

- 2) After 30 participants complete their 2nd visit at 6 months (prior to starting study drug/placebo), disease progression will be assessed using paired t-tests to determine changes between 0 and 6 month visits for each outcome measure. For the primary outcome measures, 15-F2t-isoprostane and 6MWT will be assessed for change between 0 and 6 months. This analysis will be repeated when all 6 month visits are completed.

Hypothesis: 15-F2t-isoprostane concentration will not change significantly between 0 and 6 months in RYR1-RM myopathy patients.

Hypothesis: 6MWT distance will not change significantly between 0 and 6 months in RYR1-RM patients.

The purpose of the above interim look analyses (under #1) is to confirm that the affected subjects are different from healthy individuals. Because of the rolling nature of the study and the length of time involved to complete the first phase of the study, this allows evaluate whether these outcomes are different from healthy individuals, as expected, in order to confidently proceed with the study. The purpose of the above interim look analysis (under #2) is to characterize the natural history and variability of the RYR1-RM patients for these specific outcome measures and to contribute novel data to the field of RYR1 as soon as possible for future trial design, given that an N of 30 is a large number in rare disease.

Optimal measures for fatigability in RYR1-RM will be determined using paired t-tests for 6MWT distance and speed, time for graded functional tests, and fatigue index for biodex fatigue test. Correlative analysis (Pearson correlation and/or Spearman rho) will be used to examine the linear relationship between subjective fatigue measures (FACIT and MFI) and the salivary fatigue biomarker to the objective fatigability measures mentioned above as well as to compare forced vital capacity to slow vital capacity. Spearman rho correlation, Pearson correlation and or Bland Altman analysis will also be used to examine the relationship between slow vital capacity and forced vital capacity.

Reliability will be assessed for PROMIS, FACIT, MFI, MFM, and NeuroQoL by Cronbach's alpha for internal consistency and by Intraclass correlation coefficient for test-retest. If the test-

retest analysis yields a poor correlation ($ICC < 0.40$), then the scales will not be used in the study since they are not primary outcome measures. However, if they yield moderate to high correlation, we will use the scales throughout the entire study.

Randomized, double-blind, placebo controlled, drug trial (Phase 2 of protocol):

Student's t test will be used to compare treatment to control groups. As mentioned in the Introduction, under "Summary", success of the trial will be defined as finding a significant difference in the primary oxidative stress measure of of urine 15-F2t-isoprostane between the treatment and placebo groups at the termination of the study (significantly decreased urine 15-F2t-isoprostane concentration in treatment group compared to placebo group). A sub group analysis will be performed on adults versus children given the difference in dosing. A paired t test will be used to compare subjects to their baseline values. A student's t test will be used to compare the difference in glutathione between 6 months and 12 months, between the two groups. General linear modeling will be used to control for possible confounders such as gender, age, and baseline values. Log transformed values may be used if there is no bell curve. We will use an alpha of 0.05 to determine significance.

We will use the Grounded Theory Method (GTM) of data analysis to analyze the semi-structured interview data. GTM methodically organizes unique individual experiences collected during interviews into comparable categories so that it becomes possible to find commonalities as well as variations in personal experiences. We use GTM because it is particularly effective for analyzing qualitative interview data and because it is rigorous. A GTM approach is appropriate when there is limited knowledge about a substantive area, such as the fatigue and quality of life of individuals with RYR1-related myopathy.

